## **11. CLINICAL EVALUATIONS**

IGA and acne lesion counts will be performed to document the severity of acne on the face at the Screening and Baseline visits as part of the I/E criteria. IGA will be performed again at the Final Visit (EOS). The same investigator should complete the evaluations for all subjects screened and enrolled into the study. If this becomes impossible a sub-investigator with overlapping experience with the study should complete the IGA evaluations.

### **11.1 Investigator's Global Assessment (IGA)**

Overall severity of acne on the face using a five-point scale from 0 = clear to 4 = severe will be conducted at the Screening, Baseline, and EOS visits. This is a static morphological scale that refers to a point in time and not a comparison to Baseline. Eligible subjects should also have obvious acne on the trunk (i.e., shoulder, upper chest and/or back), but these areas will not be included in the IGA.

0	Clear	Absence of active disease with no inflammatory or non-inflammatory lesions.
1	Almost Clear	Rare non-inflammatory lesions with no more than one small inflammatory lesion.
2	Mild	Some non-inflammatory lesions with no more than a few inflammatory lesions (papules/pustules only; no nodular/cystic lesions).
3	Moderate	Up to many non-inflammatory lesions and may have some inflammatory lesions but no more than one nodular/cystic lesion.
4	Severe	Up to many non-inflammatory lesions and inflammatory lesions but no more than a few nodular/cystic lesions.

### 11.2 Acne Lesion Counting

The number of inflammatory lesions (papules, pustules and nodules/cysts) and non-inflammatory lesions (open and closed comedones) on the face vertically from the hairline to mandible rim and horizontally from ear to ear, including those on the nose, will be counted at the Screening and Baseline visits. Eligible subjects must have obvious acne on the trunk (i.e., shoulder, upper chest and/or back), but the number and type of lesions on the trunk will not be counted.

Lesions are defined as follows:

- Comedones- open (blackheads) and closed (whiteheads).
- Papules- raised inflammatory lesions with no visible purulent material.
- Pustules- raised inflammatory lesions with visible purulent material.
- Nodules/cysts- Any circumscribed, inflammatory masses greater or equal to 5mm in diameter with or without cystic changes.

### 11.3 Local Skin Reactions

LSRs will be collected separately for the face and trunk. At Days 1 (before and after first application), 7, and 14, the investigator or designee will document the presence of the following LSRs known to be associated with application of topical steroids:

- Telangiectasia
- Skin atrophy
- Striae rubrae

A five-point ordinal scale will be used to assess the severity of these reactions (0 = none, 1= trace, 2 = mild, 3 = moderate, and 4 = severe).

The investigator or designee will also evaluate the severity of erythema, edema, and scaling/dryness using the five-point ordinal scales described below.

Erythema:

0	None
1	Minimal – barely perceptible erythema
2	Mild – predominantly minimal erythema (pink) in the treated area with or without a few isolated areas of more intense erythema
3	Moderate – predominantly moderate erythema (red) in the treated area with or without a few isolated areas of intense erythema (bright red)
4	Severe – predominantly intense erythema (bright red) in the treated area with or without a few isolated areas of very intense (fiery red) erythema

Edema:

0	None
1	Minimal – scant, rare edema
2	Mild – easily seen edema, minimally palpable, involving up to 1/3 of the Treatment Area
3	Moderate – easily seen edema and typically palpable, involving between 1/3 to 2/3 of the Treatment Area
4	Severe – easily seen edema, indurated in some areas, involving over 2/3 of the Treatment Area

Scaling/dryness:

0	None
1	Minimal – barely perceptible desquamation
2	Mild - limited areas of fine desquamation in up to 1/3 of the Treatment Area
3	Moderate – fine desquamation involving 1/3 to 2/3 of the Treatment Area or limited areas of coarser scaling
4	Severe – coarser scaling involving more than 2/3 of the Treatment Area or limited areas of very coarse scaling

At Days 1 (before and after first application), 7, and 14, the subject will be asked to rate the severity of any stinging/burning and pruritus that occurred in the Treatment Area using the four-point scales described below.

Stinging/burning:

0	None
1	Minimal, barely perceptible – tolerable and little discomfort
2	Moderate – tolerable, but causes some discomfort
3	Severe – very uncomfortable or intolerable

Pruritus (itching):

0	None - no evidence of itching
1	Mild - only aware of itching at times, only present when relaxing, not present when focused on other activities
2	Moderate - often aware of itching, annoying, sometimes disturbs sleep and daytime activities
3	Severe -constant itching, distressing; frequent sleep disturbance, interferes with activities

These LSRs will be collected independently of AEs. Only LSRs that require medical intervention (e.g., prescription medication) or require withholding the application of the test article will be documented as AEs. Any LSRs that are not listed above will be recorded as AEs.

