### **6.2 Instructions for Use and Application**

Mild soap will be dispensed to the subject at Visit 1/Screening, which must be used for washing the Treatment Area and other areas of the body throughout the study; the subject must, at a minimum, begin using the provided mild soap in the morning prior to the clinic visit on Day 1 (i.e., Visit 2).

The subject and parent/guardian will be instructed to wash the area(s) to be treated (i.e., face and trunk) in the morning prior to clinic visits with the mild soap and water and then dry the area gently. At the clinic, the study staff will then instruct the subject and parent/guardian on how to dispense the test article and where to apply the test article. The

“Treatment Area” will be defined at Visit 2/Baseline by the investigator as the area to which the test article is applied and will include the face and trunk. The test article will be applied to the entire face and areas of the trunk (i.e., shoulders, upper chest, and/or upper back) where acne is present. The entire 2 grams of the test article must be applied; thus, if there is still test article remaining after the affected area of the trunk is treated, the test article will be applied to the adjacent skin. The subject will be instructed to apply the test article to this same Treatment Area with each application, regardless of whether acne is still present. The percent BSA of the Treatment Area will be recorded at Baseline.

The first application of test article will be applied in the clinic under supervision of the study staff. The staff will dispense 2 grams of the test article; the subject will then be instructed (with assistance from parent/guardian, if necessary) to apply the test article to the defined Treatment Area using the “Dab, Spread, Pat” method of application. Subjects will be instructed to dab small amounts of the test article using a fingertip gently on the areas to be treated, then spread the test article to provide a thin, uniform layer over the entire Treatment Area, and finally to gently pat the skin until the test article has been absorbed into the skin. The study staff must assure that the subject (or with assistance from parent/guardian) is able to apply the test article to the entire Treatment Area (including the back).

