5 DEFINITIONS

- End of Study (EOS): Visit 4 or Early Termination Visit
- Completed Subject: A subject is considered to have completed the study if the subject completed the study treatment.
- Study Day: The study day is the day of study relative to the first dose (Baseline visit/Day 1) of the test article.
Study Day = follow-up visit date – first dose date + 1
- Baseline in Change from Baseline: The baseline assessment in change from baseline is defined as the last non-missing measurement collected at Screening or Day 1 visit prior to the test article application.
- Treatment Area: The area defined by the investigator to which the test article is applied and which includes the face and trunk.

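### Edema and extent-based scaling are scored per region but graded against face and trunk combined, so severe edema is, read literally, unreachable in at least one region of every child

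*Protocol*

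**What the plan says.** Protocol section 11.3 sets the scoring unit: "LSRs will be collected separately for the face and trunk". It then gives one set of anchors for both regions. For edema:

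- grade 2 (mild): "easily seen edema, minimally palpable, involving up to 1/3 of the Treatment Area"
- grade 3 (moderate): "easily seen edema and typically palpable, involving between 1/3 to 2/3 of the Treatment Area"
- grade 4 (severe): plainly visible edema, "indurated in some areas, involving over 2/3 of the Treatment Area"

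Scaling/dryness grades 2 to 4 use the same cut-offs of 1/3 and 2/3. Grades 3 and 4 there also have an alternative with no minimum area: limited coarser scale for grade 3, limited very coarse scale for grade 4.

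The Treatment Area is a defined term. Protocol section 6.2 describes it "as the area to which the test article is applied and will include the face and trunk", and SAP section 5 has "The area defined by the investigator to which the test article is applied and which includes the face and trunk". Its trunk part varies by child. Cream goes on the "entire face and areas of the trunk (i.e., shoulders, upper chest, and/or upper back) where acne is present", and on adjacent skin if any of the 2 g remains.

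SAP 6.4 refers back to the protocol for the scale descriptions. Neither document says that the fraction is taken within the region being scored.

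**The concern.** A score for one region is graded by a fraction of both regions together. Involvement of a given patch of skin is a smaller fraction of the combined area than of its own region, so the literal denominator can lower an extent-based grade or leave it unchanged, but never raise it. For a tolerability measure that is the unfavourable direction.

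The denominator also differs between children, because the treated trunk depends on where acne is present and how far the cream spreads. Identical facial edema could therefore meet the extent for different grades.

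LSR severity for face and trunk separately is a named secondary safety endpoint (protocol 18.2.2), tabulated by severity at each visit (SAP 7.8.4). The grades could not readily be rescaled afterwards: section 10.2 records which trunk areas were treated but only the total percent BSA, and section 12 makes photographs optional and bars their use in grading. Listed LSRs become AEs only if they need medical intervention or withholding of test article, so for most local reactions the LSR grade is the only severity record.

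**Working it through.** The plan states no figure on this point, so there is nothing to reproduce. The check is a comparison of fractions.

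**Inputs.** Cut-offs 1/3 and 2/3 (protocol 11.3). Treatment Area = face + treated trunk (protocol 6.2, SAP 5). Let f be the face share, so the trunk share is 1 − f. The documents do not give f.

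**Step 1: can both regions reach severe edema?** If a whole region is edematous and the other is clear, its involvement as a fraction of the Treatment Area equals its share. Grade 4 needs f > 2/3 for the face and 1 − f > 2/3, that is f < 1/3, for the trunk. Both cannot hold.

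**Step 2: highest edema extent met when the whole region is involved.**

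| Face share f | Face | Trunk |
|---|---|---|
| below 1/3 | mild | severe |
| 1/3 to 2/3 | moderate at most | moderate at most |
| above 2/3 | severe | mild |

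At exactly 1/3 the mild and moderate anchors touch; a share of exactly 1/3 is counted as mild here. Step 1 and the severe entries do not depend on that choice.

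**Step 3: when is whole-face edema only mild?** When f ≤ 1/3, which means a treated trunk at least twice the face. As an illustration, assume a face of 3 to 5 hand areas (1% BSA each, the protocol's handprint rule) and a treated trunk of 1 to 15. These sizes are assumptions, not from the documents.

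- Face 4, trunk 8: 4/12 = 1/3, mild.
- Face 4, trunk 2: 4/6 = 2/3, moderate, since severe needs more than 2/3.
- Face 4, trunk 1: 4/5, severe.
- The mild-only zone starts at a trunk of 6 for a 3-hand face (3/9 = 1/3) and of 10 for a 5-hand face (5/15 = 1/3).
- Over the whole grid f runs from 3/18 = 17% to 5/6 = 83%, so all three outcomes are possible.

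**Step 4: the two readings compared.** With face 4 and trunk 8, whole-face edema has an extent of 33% on the combined denominator (mild) and 4/4 = 100% on the regional one (severe). On extent alone, that is a difference of two grades for the same skin.

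**Step 5: scaling.** The extent route is limited in the same way, but grades 3 and 4 can each be reached in either region, at any f, through the alternatives that set no area minimum.

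**Step 6: after the change.** With the region as denominator, a wholly involved region has extent 100%, so the extents for grades 2 to 4 are all reachable in both regions for any f.

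**The case against.** The strongest reply is that assessors will not read the term literally. Section 11.3 opens with separate collection by region, and that governs every scale beneath it. It also asks subjects to rate stinging/burning and pruritus over the Treatment Area, although those too are reported by region, so there the term has to mean the part within the region. The erythema anchors refer loosely to treated skin in a similar way. Someone completing a face score may well judge the fraction of the face.

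That is plausible, but it is not written, and it contradicts the definition. It shows that the ceiling may not bind in practice. It does not show that graders at about six sites in two countries would all choose the same denominator.

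Other parts of the reply stand:

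- Edema going from grade 0 to 2 still counts as worsened under SAP 7.8.4, and section 6.2 keeps the Treatment Area the same at each application. The worsened versus same/improved counts are largely intact.
- The endpoint is descriptive, with a target of at least 20 evaluable children and no test. DLTs use CTCAE grades, and AE recording of LSRs does not depend on the edema grade.
- Section 15.1 places edema seventh of eight LSRs in decreasing frequency in earlier studies and describes most LSRs as minimal to mild. Scaling/dryness is third.
- The LSR form is not among the documents and may already state a regional denominator.

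**Conclusion.** The defect is real and limited. On the written definition, severe edema is unreachable for at least one region in every child, and for both when each share lies between 1/3 and 2/3. This needs no assumption about body proportions, only that the anchors are applied as worded. If some assessors use the region instead, the consequence is inconsistent grading between sites. What may be affected is the split among edema grades 2 to 4 and the extent-based scaling grades in the regional severity tables. The primary HPA and trough analyses are not touched.

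Three stronger conclusions might be inferred, and the documents do not support them:

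- *Severe scaling is also out of reach.* It is not, because limited very coarse scale qualifies without any area minimum.
- *Whole-face edema can only be mild.* This requires a face share of at most 1/3. The documents give no share, and with a small treated trunk moderate or severe is possible.
- *The trial's regional grades are capped and tolerability will look better than it is.* That depends on which denominator the sites used, which the documents do not show.

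**What to change.** In protocol 11.3, in the edema and scaling/dryness anchors, replace *of the Treatment Area* with *of the treated part of the region being scored (face or trunk)*. Make the same change on the LSR form if it repeats the anchors, and state the regional denominator in SAP 6.4.

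If data have already been collected, establish which denominator each site used and report it in the CSR. Note a possible cap on regional edema grades only where the combined area was used.

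The cost is a wording change, with no added assessment or visit. The downside is that some reactions will be graded higher than under the literal text.

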## 12. PHOTOGRAPHY

Photography documentation is not required in this study. However, the investigator may elect to photograph the subject to document the effects of treatment, AEs, or other findings during the trial. All photographs taken as part of this study are for informational purposes only and are not to assist in grading or for any other assessment.

## 13. LABORATORY TESTS

### 13.1 Blood Chemistries, Hematology, and Urinalysis

Blood and urine specimens for chemistry, hematology, and urinalysis will be collected at the Screening Visit (Days -45 to -14) and Day 14 (or at EOS / early termination) for all subjects. Laboratory test results will indicate if the subject was fasting. Screening laboratory tests will be collected with the subject fasting and EOS laboratory tests are preferred to be in a fasting state.

The following tests will be performed:

SAFETY LABORATORY TESTS		
Chemistries	Hematology	Urinalysis
Albumin	WBC	Specific gravity
Alkaline phosphatase	RBC	pH
ALT (SGPT)	Hemoglobin	Glucose
AST (SGOT)	Hematocrit	Blood
Bilirubin, total	MCV	Ketones
BUN	MCH	Microscopic analysis
CO 2 (bicarbonate)	MCHC	WBCs
Chloride	Platelet count	RBCs
Cholesterol, total	RDW	Casts
Creatinine	Differential	
Glucose	Neutrophils	
LDH	Lymphocytes	
Potassium	Eosinophils	
Sodium	Monocytes	
Total protein	Basophils	
Triglycerides		
Uric acid		
GGT		
CK		

Sample collection, handling, labeling, and shipping should be done following the instructions provided by the relevant certified laboratory and the applicable local regulations.

The investigator must review all the subject's laboratory reports in a timely manner. **Note:** The investigator will initial and date each laboratory report to indicate his/her review. The investigator will note, directly on the laboratory report, whether or not any abnormal test results are clinically significant. The investigator must complete an appropriate AE form for any new or worsening abnormal test results that are identified as clinically significant after Baseline.

AEs that may be associated with venipuncture and that must be included in the informed consent/assent include:

- Pain

- Bruising
- Bleeding at the puncture site
- Fainting
- Inflammation of the vein

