### 10.1 Visit 1 (Days -45 to -14): Screening Visit

Subjects can be screened for the study up to 45 days before Baseline. During Screening, the study requirements will be reviewed, written informed consent/assent obtained and eligibility confirmed. Screening labs will be collected with the subject fasting; if fasting laboratory tests are not possible, samples should still be collected, recording the protocol deviation. If applicable, the washout from prohibited medications or treatments will be determined and implemented. This visit will be scheduled such that the CST occurs between 7 AM and 9 AM.

*At Screening, the investigator or designee will:*

- Obtain a signed, written informed consent/assent. Subjects must provide written informed assent and be accompanied by the parent or legal guardian at the time of assent/consent signing. The parent or legal guardian must provide informed consent for the subject.
- Assign a sequential subject screening number.
- Complete demographics.
- Review eligibility criteria.
- Review and document medical/dermatological history.
- Record any prior or concomitant medications and therapies.
- Have subject complete washout from any prohibited medications, if necessary. The subject should return to the clinic to complete the remaining screening activities, if applicable. If the subject does not require a wash-out from prohibited medications and procedures, perform additional screening activities at this visit.
- Perform a dermatologic exam.
- Perform a physical exam (including vital signs, height, and weight).
- Perform a UPT for all females of childbearing potential ([Section 13.3](#)). The results must be negative for the subject to be enrolled into the study.
- Perform a 12-lead ECG.
- Collect urine and blood samples for drug and virus screens and routine safety laboratory tests (see [Sections 13.1](#) and [13.2](#)). Laboratory tests will be collected with

---

 Females of childbearing potential are defined as subjects who have experienced menarche or are 10 years of age or older.

the subject fasting; if fasting laboratory tests are not possible, samples should still be collected, recording the protocol deviation.

- Perform clinical evaluations (IGA and acne lesion counts [face only]) to determine subject eligibility (see [Section 11](#)).
- Collect PK blood draw for screening levels of plasma cortexolone 17 $\alpha$ -propionate and cortexolone concentrations (see [Section 13.4](#)).

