#### 10.4 Visit 4 (Day 14 $\pm$ 2): Final or End of Study Visit

This visit will be scheduled such that the CST occurs between 7 AM and 9 AM and within one hour ( $\pm$ 1) of the Screening CST. Laboratory test results will indicate if the subject was fasting (preferred) or not.

*At this visit, the investigator or designee will:*

- Query the subject and record any changes in health status (i.e., AEs) or concomitant medications and therapies.
- Record any LSRs (for face and trunk, separately).
- Perform clinical evaluation (IGA) (see [Section 11.1](#)).
- Perform a physical exam (including vital signs).
- Perform a CST (see [Section 13.5](#)). CST will be performed between 7 AM and 9 AM and within one hour ( $\pm$ 1) of Screening.
- Perform routine laboratory tests (see [Section 13.1](#)).
- Collect trough PK blood draw for levels of plasma cortexolone 17 $\alpha$ -propionate and cortexolone concentrations (see [Section 13.4](#)). PK blood draw will occur 12 hours ( $\pm$  30 minutes) after the evening application on the prior day.
- Perform a 12-lead ECG.
- Perform a UPT for all females of childbearing potential ([Section 13.3](#)).
- Collect and weight tube(s) of test article, as needed, and complete the Study Medication Accountability Log.
- Discharge the subject from the study, unless there is evidence of adrenal suppression.
- Note: Medication restrictions as outlined in [Section 9.1](#) are no longer required, with the exception of those medications that may affect adrenal function. Remind subjects not to use any medication that may affect adrenal axis function including topical corticosteroids (including inhaled and intranasal corticosteroids) or systemic corticosteroids (including intramuscular and intralesional injections) until the CST results are known. For those subjects with laboratory evidence of adrenal suppression, they must continue off such therapy and follow-up as designated in [Section 10.5](#).

---

 Females of childbearing potential are defined as subjects who have experienced menarche or are 10 years of age or older.

- Review safety laboratory test results including serum cortisol levels, and complete the End of Study Form, unless the subject has an abnormal HPA axis response or any laboratory tests that need to be repeated, then follow the procedures in [Section 10.5](#).

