7.4 Methods for Handling Missing Data

All summaries and analyses will use observed data only.

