7.8.6 Safety Laboratory Tests

Safety laboratory data (hematology, clinical chemistry, and urinalysis) will be tabulated at Screening and Day 14 (EOS) and Change from Baseline at Day 14 (EOS) will also be summarized. All laboratory data will be listed and reported in the units received by the central laboratory. Shift tables by analyte and by out of reference range flag (Normal, Low, and High) will be presented to facilitate the evaluation of change from Baseline to Day 14 (EOS).

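### Fasting is required for Screening chemistry but only preferred at end of study, and the glucose and triglyceride change and shift tables pool all pairs without using the recorded fasting status

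*Protocol*

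**What the plan says.** Protocol 13.1 gives the fasting rule for both visits in one sentence: "Screening laboratory tests will be collected with the subject fasting and EOS laboratory tests are preferred to be in a fasting state". Section 10.1 adds an exception at Screening: "if fasting laboratory tests are not possible, samples should still be collected, recording the protocol deviation". Section 10.4 is looser for Visit 4: "Laboratory test results will indicate if the subject was fasting (preferred) or not". It does not call a non-fasting sample at that visit a deviation.

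The status is therefore meant to be known for each sample; 13.1 also states "Laboratory test results will indicate if the subject was fasting". The chemistry panel in 13.1 includes glucose, triglycerides and total cholesterol.

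On analysis, SAP 7.8.6 says that the safety laboratory data "will be tabulated at Screening and Day 14 (EOS) and Change from Baseline at Day 14 (EOS) will also be summarized", and "Shift tables by analyte and by out of reference range flag (Normal, Low, and High) will be presented". Protocol 18.3.3.3 plans the same for the Safety population. SAP section 5 defines baseline as "defined as the last non-missing measurement collected at Screening or Day 1 visit prior to the test article application". Both schedules of events place safety laboratory tests only at Screening and Visit 4, so baseline is in effect the Screening sample. SAP 7.4 adds "All summaries and analyses will use observed data only", and SAP 7.10 plans no subgroup analyses. The SAP mentions fasting only in a footnote to its schedule table, and in no analysis section.

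**The concern.** The change from Screening to EOS is the only comparison available for the laboratory data, because every child receives the test article and there is no control arm in which a meal effect could cancel. If more children have eaten before the EOS sample than before the Screening sample, part of the mean change in glucose or triglycerides reflects food, and some Normal-to-High shifts may too. The ambiguity also runs the other way: if the tables do not separate fasting from non-fasting pairs, a genuine rise is easier to put down to a meal.

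Safety laboratory testing is a named secondary safety endpoint (protocol 18.2.2), and protocol section 2 treats systemic safety as a reason for the study. In a study this small, a few non-fasting samples can visibly change a shift table.

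**Working it through.** The documents state no figure on this point, so there is nothing to reproduce. The algebra below shows how the meal component behaves.

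**Inputs from the documents**
- Pairs: up to about 24, the approximate enrolment in protocol 14.4. The laboratory tables use the Safety population, so this is the relevant number rather than the 20 evaluable subjects.
- Non-fasting samples are possible at both visits (10.1 and 10.4), and nothing in SAP 7.2.1 or 7.8.6 removes them from the tables.

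**Inputs that are assumptions**
- qS and qE, the non-fasting shares at Screening and EOS.
- D, the meal effect on the analyte. For illustration: 20 to 60 mg/dL for triglycerides and 5 to 20 mg/dL for glucose.
- Fasting status at the two visits is treated as independent when pairs are counted.

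**Formulas**
- Meal component of the mean change = (qE − qS) × D.
- Fasting-to-fed pairs = n(1 − qS)qE. Fed-to-fasting pairs = n·qS(1 − qE).

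**Results with n = 24**

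| qS | qE | Fasting-to-fed pairs | Fed-to-fasting pairs | Meal component |
|---|---|---|---|---|
| 0 | 10% | 2.4 | 0 | 0.10D |
| 0 | 25% | 6.0 | 0 | 0.25D |
| 0 | 50% | 12.0 | 0 | 0.50D |
| 10% | 25% | 5.4 | 1.8 | 0.15D |
| 10% | 10% | 2.2 | 2.2 | 0 |
| 10% | 0 | 0 | 2.4 | −0.10D |

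For the fourth row: 24 × 0.90 × 0.25 = 5.4, 24 × 0.10 × 0.75 = 1.8, and (5.4 − 1.8)/24 = 0.15.

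**In units, with qS = 0.** This is the largest component for a given qE.
- Triglycerides: 0.10 × 20 = 2 to 0.50 × 60 = 30 mg/dL.
- Glucose: 0.10 × 5 = 0.5 to 0.50 × 20 = 10 mg/dL.

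With qS = 10% and qE = 25%, the component falls to 0.15 × 20 = 3 to 0.15 × 60 = 9 mg/dL for triglycerides, and to 0.15 × 5 = 0.75 to 0.15 × 20 = 3 mg/dL for glucose.

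**Shift tables.** One child is 1/24 = 4.2 percentage points.

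**Chance of at least one non-fasting EOS sample among 24.** 1 − 0.90^24 = 92% if qE = 10%, and 1 − 0.75^24 = 99.9% if qE = 25%.

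**After restriction to pairs fasting at both visits.** The meal component is 0. With qS = 0, the pairs left are 24 × 0.90 ≈ 22, 24 × 0.75 = 18 and 24 × 0.50 = 12 for qE = 10%, 25% and 50%.

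**The case against.** A reader might infer that the artefact runs one way only, with every child fasted before and possibly fed after. The documents do not support that. Section 10.1 allows non-fasting Screening samples, and they stay in the Safety population tables. Fed-to-fasting pairs can therefore occur, and the net effect is zero when qE = qS and negative when qS > qE.

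The size is also unknown. The unit ranges above span 15-fold for triglycerides and 20-fold for glucose, and every input behind them is assumed. Visit 4 is an early-morning visit built around a cosyntropin test between 7 and 9 AM, with fasting preferred, so the non-fasting share may be low. That is fair, but early attendance is not an instruction to fast, and protocol 13.5 makes the time window at that visit an ideal only.

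The tables are descriptive, secondary and tied to no decision rule; metabolic effects are not a study objective. This stands, and it limits the weight of the point.

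Finally, under 13.1 and 15.3 the investigator reviews each report and records clinically significant abnormalities as adverse events, and all laboratory data are listed. A non-fasting result can thus be interpreted child by child. That protects the individual assessment but does not correct the summary tables. Nor does the SAP say that the fasting flag will appear in the listing.

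**Conclusion.** The point holds in a limited form. The fasting rules differ between the two visits, the status is recorded, and the analysis plan does not use it. The glucose and triglyceride summaries can therefore include a meal component of (qE − qS) × D that no control arm removes. It is upward if non-fasting is commoner at EOS, which the asymmetric rules make likely but do not guarantee; pairs that differ in either direction also add noise. Its size cannot be stated from the documents, because qE, qS and D are all absent.

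It would be wrong to read this as a flaw in the main results. The HPA and trough endpoints are untouched, and only descriptive secondary safety tables for two analytes are concerned. It is worth correcting because the correction is cheap and is best specified before the data are seen.

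**What to change.** In SAP 7.8.6, state that for glucose and triglycerides the change-from-baseline and shift tables (within Tables 14.3.9.2 and 14.3.9.5) are based on pairs flagged fasting at both Screening and Day 14/EOS, with n shown. Keep the all-pairs versions as supportive, and show the fasting flag beside each result in Listing 16.2.12.2.

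This takes a sentence or two and a listing column, using a status the protocol already requires. It needs no new samples or visits. The cost is fewer pairs for two analytes in the main table, as counted above; the all-pairs tables keep the rest visible.

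Optionally, reconcile the fasting wording for Screening and Visit 4 across protocol 10.1, 10.4 and 13.1.
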